 - a. Determine if F18-NaF signal correlates with CCTA defined plaque volume and CAC score.
 - b. Determine the change in F18-NaF signal in relationship to statin therapy.

In order to achieve the primary aim, we will evaluate men (age 40-75) and women (age 40-75) with a screening/ baseline CT scan of the coronary arteries. Study subjects will be followed over time if they a) have noncalcified coronary artery plaque, b) have not been treated with GRCR defined high intensity statin treatment for more than 90 days prior to enrollment and c) agree to receive high intensity statin treatment. The study duration will be 36 months. Subjects eligible based off their screening/baseline CT scan of the coronary arteries will receive Rosuvastatin or another high intensity statin treatment. Study subjects will also undergo CMR scan to detect T1 high signal intensity plaque and for comprehensive cardiovascular phenotyping. Correlation of NaF signal on PET scanning will also be performed.

For the primary aim, subjects fulfilling basic inclusion/exclusion criteria and giving informed consent to the study will be examined using CT angiography (3rd generation CT scanner, advanced dose reduction techniques). If noncalcified plaque is present, the subject will have follow-up CCTA at 12, 24 and 36 months. Additional correlative testing is detailed in the study calendar. The primary outcome parameter is change in noncalcified plaque volume. Noncalcified plaque volume will be assessed based on the largest noncalcified atheroma at baseline CCTA.

OVERVIEW OF ENROLLMENT

[figure not shown]

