The use of short acting nitrates (i.e. sublingual nitroglycerine) will be used according to NHLBI and CC standards for CCTA for study subjects with systolic blood pressure >100mmHg to allow for accurate assessment of the degree of coronary artery stenosis, reduce vasospasm and to standardize vasomotor tone. Potential contraindications to nitroglycerine use should be reviewed prior to administration (known

allergy or severe intolerance, critical aortic stenosis, pre-existing hypotension, prior PDE5 (e.g. sildenafil) use. If the patient cannot receive nitroglycerine (due to intolerance, borderline blood pressure, investigator judgment, contraindication), the patient may still proceed with the study. Known risks of nitroglycerine use include headache, reduction in blood pressure, hypotension.

CT image analysis

CT angiogram images will be reconstructed and post-processed on a separate workstation using dedicated CCTA software. Readers will be blinded as to subject and date of the CT angiogram examination.

Coronary calcification

Coronary calcification will be measured by the Agatston (Agatston, Janowitz et al. 1990) method. The volume, calcium mass and a voxel based calcium density analysis will also be performed. Total coronary artery calcium scores will be generated by summing the values from the left main, left anterior descending, left circumflex and right coronary arteries.

Total plaque quantification

Raw data will be reconstructed at approximately 0.5 mm slice-thickness. The baseline axial MDCT images with adequate reconstruction phase will be post processed and analyzed by commercial software (e.g. Medis QAngioCT). Lumen and wall boundaries of target vessels will be semi-automatically detected on cross sectional images. Under the guide of multiplanar reconstructed images, experienced readers will review and edit lumen and outer wall contours of coronary segments of the left anterior descending coronary artery (LAD), left circumflex coronary artery (LCX) and right coronary artery (RCA) from ostium to vessel diameter < 2.0mm from cross sectional image. Segments with artifact or blur will be excluded. Volume estimates of plaque extent are obtained by multiplying cross sectional area of plaque by slice thickness. Plaque wall volume is computed by subtracting lumen volume from vessel volume.

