6. STATISTICAL CONSIDERATIONS

Primary Endpoint: The primary endpoint of this study is the change in noncalcified plaque volume after 24 months.

Secondary Endpoints: In addition to the 24 months follow-up period specified for the primary endpoint, we plan to follow the patients for an extended period of 12 months to study the long term effects of the statin therapy. As a result, the patients will be followed for a total of 36 months with the first 24 months for the primary endpoint and the additional 12 months for the secondary endpoints. The secondary endpoints include:

- 1) Change in noncalcified plaque volume assessed by CCTA at the end of 36 months;
- 2) Effects of covariates including age, sex, race, body mass index and baseline plaque volume on the change of plaque volume measured by CCTA at 24 and 36 months.

- 3) The relationship of CMR T1 high signal intensity plaque and change in T1 signal by CMR over time to CCTA plaque characteristics.
- 4) (Pilot study): the relationship of coronary artery plaque by CCTA to sodium fluoride (F18-NaF) uptake using positron emission tomography (PET) scanning:
 - a. Determine if F18-NaF signal correlates with CCTA defined plaque volume and CAC score.
 - b. Determine the change in F18-NaF signal in relationship to statin therapy

Preliminary Information: One study in the literature was conducted as a pilot study with similar goals (Burgstahler et al. 2007). This pilot study investigated 22 noncalcified plaques in 12 patients before and after lipid lower therapy for 18 months. The mean patient age (61) and cardiovascular risk profile was similar to that expected in our cohort. The medication used was atorvastatin 20 mg. The mean (\pm sd) volume of all plaques was reduced by statin therapy from 0.042 ± 0.029 mL to 0.030 ± 0.014 mL ($P < 0.05$). The mean reduction of plaque volume was 0.012 mL with the standard deviation 0.017 mL.

Statistical Hypotheses: Because the study of Burgstahler et al. (2007) is based on a small sample size, we would like to consider a somewhat conservative assumption on the mean and sd for the plaque volume reduction than the preliminary information provided by this study. Specifically, we hypothesize that the patients with high intensity statin treatment will have at least 0.008 mL mean reduction of plaque volume at the end of the 24 months treatment period. Let

$$\Delta = \text{mean reduction of plaque volume at 24 months.}$$

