- 4) **Secondary analysis of the above patients:** In addition to the ITT and missing data approaches mentioned in 1)-3), our secondary analysis of the primary endpoint (change of plaque volume between baseline and 36 months) will also include: a) non-ITT approach of including only treatment compliant patients in the analysis, b) complete data approach of using only patients with observed plaque volumes in both baseline and 36 months. As a sensitivity analysis, we will compare the results obtained from a) and b) above with the primary analysis of 1)-3). This sensitivity analysis will provide useful insights into the characteristics of the patients with noncompliance and/or missing plaque volume data at 24 and 36 months.

Secondary Analysis with Subgroups and Covariates: Regression models will be considered for the analysis of secondary endpoints.

- 1) **Cross-Sectional Data:** Regression models with cross-sectional outcome and covariates, i.e. data without repeated measurements over time, will include multivariable linear and nonlinear models. Nonparametric smoothing methods, such as splines and local polynomials, will be used to explore the relationships between the outcome and covariates. The flexible ANOVA F Goodness-of-Fit tests will be used to test the adequacy of the parametric linear and nonlinear regression models.
- 2) **Longitudinal Outcome and Covariate Data:** For data including repeatedly measured outcome and/or covariates over time, we will consider the commonly used linear and nonlinear mixed effects models to explore the time trends of the outcome variables and corresponding covariate effects. Similar to the exploratory analysis with cross-sectional data, we will also consider the flexible nonparametric longitudinal regression methods, such as the time-varying coefficient models and models of functional data analysis, to evaluate the appropriateness of the parametric mixed effects models.

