Atherosclerosis and concomitant cardiovascular events are the leading cause of death in all major racial/ethnic subgroups in industrialized nations. Efforts to reduce the burden of cardiovascular disease are relevant to persons of all ethnicities. Our planned enrollment has been selected to be representative of the general gender and ethnic demographic subgroups of the greater Washington DC area.

Reproducibility Sub study (No longer recruiting after Amendment O Protocol dated 7/02/2020)

A subgroup of 30 participants who had CCTA defined coronary plaque will be asked to return 4 weeks after their initial CCTA scan for a second CT study using the same CCTA protocol. Additionally, the initial CCTA and reproducibility CCTA will be in accordance for total annual radiation dose exposure at the NIH as determined by the radiation safety committee. Eight to twelve patients will be selected from three groups: (a) patients with a calcium score of 0-99, (b) patients with a calcium score -100-399 and (c) patients with a calcium score of > 400. These 30 scans will be interpreted by two readers, allowing assessment of both intra and interobserver variability as well as repeatability limits.

Subjects who participate in the Reproducibility sub study will not have the cardiac MRI performed.

7.2. PARTICIPATION OF CHILDREN:

Atherosclerotic disease is not a disease of childhood and children will not be eligible for participation in this study, based on the fact they are unlikely to have this disease.

7.3. EXCLUSION OF PREGNANT WOMEN:

The risk from radiation exposure is increased in children and especially in the fetus. This can be explained by a higher rate of mitosis earlier in life (Hall 2009, Goodman and Amurao 2012). It is generally conceived that X-ray imaging should be only used in vital indications in pregnant women. In the context of this study this is not the case and therefore pregnancy is an exclusion criteria (§46.204 Code of Federal Regulations. Condition “Any risk is the least possible for achieving the objectives of the research” is not met)

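### Secondary endpoint 2 relates change in plaque volume to the same baseline reading from which change is computed, with no measurement-error correction and no statement of how baseline enters the model

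*Combined protocol and SAP*

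**What the plan says.** Secondary endpoint 2 appears in the same terms in Section 1 (under the primary aim and again under Design) and in Section 6. It concerns the effects of demographic covariates, body mass index and "baseline plaque volume on the change of plaque volume measured by CCTA at 24 and 36 months".

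The method is left open. Under Secondary Analysis with Subgroups and Covariates, Section 6 says "Regression models will be considered for the analysis of secondary endpoints". Item 1 there lists linear, nonlinear, spline and local polynomial models. Item 2 adds "linear and nonlinear mixed effects models to explore the time trends of the outcome variables and corresponding covariate effects". Neither item mentions measurement error, regression to the mean, or whether baseline volume is a predictor or one of the repeated outcomes.

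The volume is not read without error. Contours are found semi-automatically and then "experienced readers will review and edit lumen and outer wall contours of coronary segments" (Section 1, CT image analysis). The lesion is chosen on the baseline scan: "Noncalcified plaque volume will be assessed based on the largest noncalcified atheroma at baseline CCTA".

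Section 7.1 describes a repeat-CCTA sub-study of 30 participants read by two readers, "allowing assessment of both intra and interobserver variability as well as repeatability limits". No section feeds its result into endpoint 2.

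**The concern.** Change is follow-up minus baseline, so the baseline reading error enters the predictor with a plus sign and the outcome with a minus sign. A lesion that happens to be over-read at baseline looks large and then appears to shrink. This produces a negative slope even when true change has nothing to do with true size. A larger sample or a more flexible curve does not remove it. Section 6 defines the effect as a reduction, and on that scale the same artefact has a positive sign.

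Endpoint 2 is the trial's means of explaining why response differs between patients, which Section 1 gives as part of its motivation. A statement that larger plaques regress more could be wholly or partly an artefact. Coefficients of covariates associated with baseline volume would also be distorted. Section 1 reports that age, gender and body mass index were associated with plaque volume in the investigators' earlier diabetic cohort.

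**Working it through.** **The plan's own figure.** The documents give no figure for endpoint 2. The primary sample size reproduces: (0.03 × (1.960 + 1.282) / 0.008)² = 147.8, or 150 with the t distribution. The Lan-DeMets O'Brien-Fleming inflation of 1.0034 brings 150 to 150.5, hence 151 as stated.

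**Inputs.**
- Baseline SD 0.029 mL, from the pilot in Section 6 ("volume of all plaques was reduced by statin therapy from 0.042 ± 0.029 mL to 0.030 ± 0.014 mL").
- SD of change 0.03 mL (planning value) or 0.017 mL (pilot), both from Section 6.
- n = 151 at 24 months, from Section 6.
- Scan-error variance: not given. Assumed to make up a share s of the variance of change.

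**Model.** Observed baseline X = T + e0 and follow-up = T + D + e1. The errors are independent with equal variance Ve, and reliability is λ = 1 - Ve/Var(X). If the true slope of D on T is β, the slope of (follow-up - X) on X has expectation λβ - (1 - λ). With β = 0 this is -(1 - λ).

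Change contains two errors, so Ve = s × SD(change)²/2, and the false slope is -[s × SD(change)²/2] / 0.029².

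- SD of change 0.03: -(s × 0.00045)/0.000841 = -0.535 s.
- SD of change 0.017: -(s × 0.0001445)/0.000841 = -0.172 s.

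**Chance of a false p<0.05.** The standard error of the slope is √(SD(change)² - slope² × 0.029²) / (0.029 × √151), where 0.029 × √151 = 0.356. Example for SD 0.017 and s = 50%: √(0.000289 - 0.0859² × 0.000841) = 0.0168. The standard error is then 0.0168/0.356 = 0.047 and the expected t is -0.086/0.047 = -1.82. Against a critical value of 1.98 this gives about 44%. Simulation of 20,000 trials per setting, with true change independent of true baseline, agrees:

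| Error share s | Slope, SD 0.03 | False p<0.05 | Slope, SD 0.017 | False p<0.05 |
|---|---|---|---|---|
| 10% | -0.05 | about 10% | -0.02 | about 6% |
| 25% | -0.13 | about 35% | -0.04 | about 15% |
| 50% | -0.27 | about 90% | -0.09 | about 44% |
| 100% | -0.54 | about 100% | -0.17 | about 96% |

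**Does a correction work?** The corrected slope (b + 1 - λ)/λ had a mean within 0.002 of zero in all eight settings.

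**Does Oldham's method work?** It regresses change on the mean of the two volumes. With SD of change 0.03 it gave false slopes of +0.35 (over 99% rejection) at s = 25% and +0.27 (about 90%) at s = 50%. It was null only at s = 100%, where no patient's true response differs from another's.

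**Precision of the error variance.** With 30 repeat pairs (30 degrees of freedom), the 95% interval runs from 30/46.98 = 0.64 to 30/16.79 = 1.79 times the estimate. As an illustration, an estimated 1 - λ of 0.20 would have a range of about 0.13 to 0.36.

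**The case against.** The strongest reply is that the plan does not commit to the faulty regression. It says models will be considered, and it includes mixed models for scans at 0, 12, 24 and 36 months. With baseline as one of the outcomes, such a model can separate scan error from true level. Section 6 refers to this work as exploratory, and endpoint 2 has no stated alpha or power. All of this stands, and it makes the fault partly one of underspecification. It does not remove the fault, because the endpoint itself lists baseline volume among the covariates and no text steers the analyst away from the naive model.

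The second reply concerns size, and it also stands. The planning SD of 0.03 mL is deliberately conservative, and pairing it with the pilot baseline SD enlarges the artefact. The 0.029 mL comes from 22 plaques in 12 patients, whereas this trial measures one index lesion per patient. A larger SD for that lesion would shrink the effect: at an assumed 0.05 mL with SD of change 0.03, the false-positive rates fall to about 15%, 45% and 97%. The 100% share is a limit rather than an expectation, because Section 1 expects true response to vary.

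A reader might therefore infer that the trial will very likely report a false baseline effect. The documents do not support that, since no scan-error SD is given and the rate is only about 6% to 10% at a 10% share. A reader might also take the pilot's own SDs as proof of the artefact. They imply a correlation of (0.029² + 0.014² - 0.017²)/(2 × 0.029 × 0.014) = 0.92 and a slope of 0.92 × 0.014/0.029 - 1 = -0.56. That slope mixes any true effect with the artefact and cannot be split without an error variance.

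**Conclusion.** The concern holds as a conditional bias in a named secondary endpoint. If observed baseline volume is used as a covariate for change, the slope with no true relation is -(1 - λ). It lies anywhere from near zero to -0.54 over the assumed range of scan error and the two SDs of change in the documents. The direction is certain under independent reading errors; the size is not. Choosing the largest lesion at baseline would add regression to the mean in the same direction, and this was not quantified. The distortion of the age, sex and body mass index coefficients follows from the same mechanism and was not sized either. The 36-month analysis has the same structure, but its sample size is not stated.

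It would be wrong to carry this over to the primary endpoint. The test of mean change and its n of 151 do not depend on this regression. The point is one the SAP should settle, not a threat to the main result.

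**What to change.** For the baseline-volume effect, pre-specify one of two analyses:

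1. An errors-in-variables correction (the reliability correction above, regression calibration or SIMEX), applied in the model with the other covariates so that their coefficients are corrected too.
2. A joint longitudinal mixed model in which the baseline scan is an outcome, with the baseline effect read from the relation between true level and true change.

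Take the scan-error variance from whatever repeat-CCTA pairs the reproducibility sub-study obtained. Recruitment to it closed after Amendment O, and the number achieved is not stated. Participants were to be chosen by calcium-score group, so carry over the error variance and compute λ with the main trial's own index-lesion variance. Propagate the uncertainty of that variance into the confidence interval, and show results over a range of λ. Report the uncorrected slope as descriptive only.

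Do not use Oldham's method as a substitute. When true response varies between patients it creates a false slope of the opposite sign.

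The cost is SAP wording, a little more analysis work and a wider confidence interval. No new scans or patients are needed.

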Software: Sample sizes and stopping boundaries of the group sequential design are computed using the R “gsDesign” package, version 3.1.3 (2015-03-09). Details of the statistical methods and theory of the design are described in C. Jennison and B. W. Turnbull (2000, “Group Sequential Methods with Applications to Clinical Trials”, Chapman and Hall/CRC, Boca Raton, FL).

Figure. Stopping boundaries with one interim look based on the Lan-DeMets O’Brien-Fleming approximate spending function.

Noncompliance and Missing Data: Given our past experience in similar clinical trials, we do not anticipate noncompliance as a major problem. However, despite the best possible effort, there are inevitably noncompliant patients and/or patients with missing data. We categorize the noncompliance and missing data into the following three situations:

- 1) **Noncompliant patients with complete follow-up examinations at baseline and 24 months:** The primary analysis of these patients, including both the interim analysis and the final analysis of the primary endpoint, will be carried out using the intent-to-treat (ITT) principle. Under the ITT principle, the observed plaque volumes at baseline and 24 months from these patients will be included in the primary analysis.
- 2) **Noncompliant patients with missing examinations at 24 months:** Since plaque volume normally does not decrease without significant intervention, we will apply the ITT principle to these patients using the approach of setting their plaque volumes at 24 months to be the same as their baseline values.
- 3) **Compliant patients with missing examination at 24 months:** We expect that only a small portion of the patients will fall into this category, since our study coordinators will give their best efforts to contact and keep track these patients. For the primary analysis, we will include these patients using the same approach as 2) by setting their plaque volumes at 24 months to be the same as their baseline values.

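### Patients without a 24-month scan are scored as zero change, the planned checks of that rule are written for 36 months, and the analysis set for the final test is not settled

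*Combined protocol and SAP*

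**What the plan says.** All references are to the combined protocol and SAP.

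- **Endpoint.** Section 6 states: "The primary endpoint of this study is the change in noncalcified plaque volume after 24 months". The Primary Aim in section 1 and the Design section agree. Change at 36 months is a secondary endpoint.
- **Final test.** Section 6, Final Analysis, computes Z2 on 151 patients who have completed 24 months. Sample Size Justification allows about 20% dropout and so enrols 190.
- **Noncompliance and Missing Data, item 2.** Noncompliant patients without a 24-month scan enter the primary analysis by "using the approach of setting their plaque volumes at 24 months to be the same as their baseline values". The reason given is: "Since plaque volume normally does not decrease without significant intervention".
- **Item 3.** Compliant patients without the scan get the same treatment. The only comment concerns frequency: "We expect that only a small portion of the patients will fall into this category". The section also opens with "we do not anticipate noncompliance as a major problem", so the expected split of missing patients between items 2 and 3 is not fixed.
- **Item 4.** The checks are introduced as "our secondary analysis of the primary endpoint (change of plaque volume between baseline and 36 months"). Check a) keeps compliant patients only and names no time point of its own. Check b) is a "complete data approach of using only patients with observed plaque volumes in both baseline and 36 months". Both are to be compared with the primary analysis of items 1 to 3.
- **Mixed models.** These appear under Secondary Analysis with Subgroups and Covariates, which opens: "Regression models will be considered for the analysis of secondary endpoints". They are not named as a check on the zero-change rule.

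**The concern.** The trial has a single arm, so the mean 24-month change and its interval are the result. There is no control group in which an imputation error could cancel. At the planned dropout, about one patient in five would carry an assumed zero.

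The stated reason covers half of one group. It argues against shrinkage in untreated patients. It does not argue against growth in them, and it cannot carry over to patients who took the treatment.

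The checks meant to show whether the rule matters are written for another time point. A 36-month complete-data result set against a 24-month zero-filled result mixes the missing-data question with a further year of treatment. Finally, a reader cannot tell whether the headline estimate will come from the completers or from everyone enrolled.

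**Working it through.** **Inputs.** From section 6: mean reduction 0.008 mL, SD 0.03 mL, two-sided 5%, power 90%, one interim look at about half the information, 151 completers, 190 enrolled. Missing at 24 months: 190 - 151 = 39 (20.5%). From Table 2 in section 1: growth of 9% to 20% a year. Assumed: a baseline lesion of 0.042 mL, which is the mean of the 22 plaques in the pilot study cited in section 6, with 0.025 to 0.08 mL as a range because this trial measures the largest noncalcified lesion.

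**1. The plan's own figures.**
- Fixed-sample n = (0.03 × (1.960 + 1.282) / 0.008)² = 147.8; with the t distribution, 150.
- Lan-DeMets O'Brien-Fleming bounds at half information are 2.963 and 1.969, matching 2.96 and 1.97. The sample-size inflation is 1.0084, and 150 × 1.0084 = 151.3, matching 151.
- 151 / 0.8 = 189, against 190 stated.

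The figures reproduce when 151 means patients with an observed scan.

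**2. The two readings of Z2.**
- Completers: mean 0.0080; SE = 0.03 / √151 = 0.00244; power 90.5%.
- All 190 with 39 zeros: mean = 151 × 0.008 / 190 = 0.00636; SD = √(0.795 × (0.03² + 0.008²) - 0.00636²) = 0.0269; SE = 0.0269 / √190 = 0.00195; power 90.1%.

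**3. Bias of the zero-filled mean.** With n noncompliant patients among the 39, the true all-patient mean is ((190 - n) × 0.008 - n × growth) / 190, where growth = baseline × 2 × annual rate. The rule reports 0.00636 whatever the mix.

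| Mix of the 39 (0.042 mL baseline) | True mean, mL | Bias | 95% CI coverage |
|---|---|---|---|
| All compliant, responding like completers | 0.0080 | -20.5% | 87% |
| All noncompliant, stable | 0.0064 | 0% | 95% |
| All noncompliant, 2%/year | 0.0060 | +6% | 95% |
| All noncompliant, 9%/year | 0.0048 | +32% | 88% |
| 10 compliant, 29 noncompliant, 5%/year | 0.0061 | +4% | 95% |

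For the 9% row with all 39 noncompliant: growth = 0.042 × 2 × 0.09 = 0.00756; (151 × 0.008 - 39 × 0.00756) / 190 = 0.0048; 0.00636 / 0.0048 gives +32%. The same row with a 0.025 mL baseline gives +17%, and with 0.08 mL gives +87%. Coverage was simulated. It agrees with the normal formula using the sampling SD 0.03 × √151 / 190 = 0.00194.

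The two errors cancel when n = 39 × 0.008 / (0.008 + growth), which is 20 of 39 at 9% a year.

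**4. Tipping point.** Take completers exactly as planned and all 39 noncompliant, each with a fixed increase s. Then Z2 = mean / SE falls to 1.97 at s = 0.0116 mL. That is 0.0116 / (2 × 0.042) = 13.8% a year, or 23.1% and 7.2% for baselines of 0.025 and 0.08 mL. The tip can therefore lie inside the growth range that the protocol cites.

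**5. What the checks could show.** Moved to 24 months, both checks still only drop patients. Neither assigns growth to a patient who was not scanned.

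**The case against.** **A slip in one number.** Item 4 compares its checks with the 24-month primary analysis and ends by mentioning missing data at both 24 and 36 months, so 36 may be an error for 24. That is plausible. As written, though, no 24-month check is defined, and the text needs correcting either way.

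**The analysis set.** The document never calls 190 an analysis set. The 151 can be read as a planning count, with the missing-data text governing. That is a fair reading, but one sentence is needed to say so. Only item 1 mentions the interim analysis, so it is also open whether zero-filled patients count towards the 76.

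**Large biases are corner cases.** This stands. Section 3.4.1 lets patients who stop treatment continue imaging, which moves them to item 1, and returns them to usual care. The 20% rate comes from a placebo arm of HIV-positive patients.

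A reader might also infer the following, which the documents do not support:

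- *Zero contradicts the hypothesised 0.008 mL.* That figure is the alternative to be detected, not a fact about missing patients. The gap in item 3 is a missing justification.
- *Power is lost.* With all 190 analysed it stays about 90%. It would be 82.8% only if 151 were the total including 20% zeros, and the dropout inflation does not imply that. The test also keeps its 5% level if missing patients average no change.
- *The primary result depends on who is labelled noncompliant.* Items 2 and 3 apply the same rule, so at present it does not.
- *Compliant patients must be imputed in the primary analysis.* With 20 of 39 noncompliant and growing 9% a year, doing so gives a bias of +13%, against 0% under the present rule.

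**Conclusion.** The point holds as a fault in the estimate and its checks, not in the test. Two parts rest on the text alone: the checks of a 24-month endpoint are framed at 36 months, and the final test is described both on completers and with non-completers added. The second moves the planned estimate from 0.0080 to 0.0064 mL.

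The zero-change rule itself is an assumption with incomplete support. Its bias can be negative, nil or positive: -20% to +32% across the all-compliant, all-stable and all-growing-9% cases at an assumed 0.042 mL baseline. Those ends are extreme mixes, and with slow growth and few compliant dropouts the effect is small. The growth figures rest on the assumed baseline, constant annual growth and 39 missing patients. What matters is that no stated 24-month analysis would show which case applies. This should be fixed before the analysis; confidence in the size of the bias is medium.

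**What to change.** 1. In section 6, item 4, define the compliant-only and complete-data checks of the primary endpoint on change from baseline to 24 months. Keep any 36-month versions for the 36-month secondary endpoint.
2. State one analysis set for Z1 and Z2, reconciling Interim Analysis and Final Analysis with items 1 to 3, and say whether zero-filled patients count towards the 76 and the 151.
3. Describe zero change as an assumption, and report two 24-month sensitivity analyses beside it:
   - for compliant patients without the scan, multiple imputation or an equivalent likelihood analysis that uses the scheduled 12-month scans;
   - for noncompliant patients without it, a tipping-point analysis over growth of 0% to 20% a year.
4. Define noncompliance in advance, because check a) and both new analyses need it; no threshold was found in the documents.

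Replacing zero for compliant patients in the primary analysis is optional. It would make the main estimate depend on that label and can remove a partial cancellation of errors.

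The cost is SAP wording and a little more analysis, with no new scans and no change in sample size.
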